### **8.8.3 Concomitant Medications**

Frequency and incidence of concomitant medications will be displayed by generic name, sorted by class, and summarized by treatment group, analysis set, and category. Concomitant medications taken on Day 0 (Experimental Session), Day 1, Day 2 after IMP administration will be presented separately. Any psychiatric concomitant medications will be tabulated by period (Preparatory, Treatment Period, Follow-up Period). Frequency and incidence of positive or serious ideation and suicidal behavior will be presented using descriptive statistics of C-SSRS scores in tabular format. Vital signs (heart rate, blood pressure, and body temperature) for Experimental Sessions will be summarized using descriptive statistics in tabular format listing values at pre-IMP administration, prior to the supplemental dose, and at the end of each Experimental Session.

### **8.8.4 Analysis of Suicidal Ideation and Behavior**

Suicidal ideation and behavior will be summarized according to suggestions made in the C-SSRS Scoring and Data Analysis Guide [1]. A positive response for suicidal ideation is counted when a participant answers “yes” to any one of the five suicidal ideation questions (Categories 1-5) on the C-SSRS (i.e., a score >0 for suicidal ideation). Serious suicidal ideation is a suicidal ideation score of 4 or 5. A positive response for suicidal behavior occurs when a participant answers “yes” to any one of the five suicidal behavior questions (Categories 6-10) on the C-SSRS (i.e., a score >0 for suicidal behavior). The number and percent of positive responses of Positive Ideation, Serious Ideation, and Positive Behavior will be tabulated by treatment group and time period (lifetime, screening, baseline, each Experimental Session (pre- and post-IP), Integrative Sessions, and endpoints). Frequency and incidence of positive or serious ideation and suicidal behavior will be presented using descriptive statistics in tabular format.

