Suicidal ideation and behavior are disease related events with high incidence in populations of people with PTSD, especially those suffering from chronic PTSD. Due to the nature of the therapeutic method, wherein a person may re-experience emotions associated with the traumatic event in order to reprocess the memory in a new, therapeutic way, thoughts of ending one's life may surface during the process. In previous MAPSsponsored clinical trials C-SSRS scores have escalated during the Preparatory Sessions, which is thought to be a result of preparatory discussion of traumatic experiences, and/or participants concomitant tapering off long-prescribed medications, such as SSRIs and benzodiazepines. During both non-drug and MDMAassisted therapy sessions, participants are asked to think about and discuss their experiences, thoughts, and emotions related to their condition. Participants are also asked to report on their suicidality in these sessions and follow-up phone calls through C-SSRS administration. They may experience intense emotional responses to recalling and speaking about this material. As MDMA is only administered in combination with therapy, the distress associated with therapy is unavoidable and is considered a necessary part of the therapeutic process that requires proper facilitation and support from

therapists.

- Therapy teams minimize risks by carefully evaluating all participants to determine if there is a current risk of suicidal behavior. Participants with current, severe suicidal ideation or a suicide attempt within the past six months are excluded from the trial, see Section 3.2
 Exclusion Criteria. However, participants with a history of suicide attempts are not excluded unless significant risk of suicidal behavior is present at the time of Screening, as this would result in enrolling a non-representative sample of the population.
- If positive serious ideation or behavior occurred after study enrollment, the investigators are to make additional follow-up C-SSRS observations to ensure participant safety and to track scores until they returned to non-serious levels.
- Should a participant be at serious risk to themselves, then the therapy team and site staff will intervene appropriately, consistent with professional practice standards. In extreme circumstances, this may involve summoning external crisis management teams for further assessment which may lead to involuntary hospitalization.

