### **3.3 Safety Objectives**

The overall safety objective is to assess severity, incidence and frequency of Adverse Events (AEs), Treatment Emergent AEs (TEAEs), AEs of Special Interest (AESIs), and Serious Adverse Events (SAEs), concomitant medication use, suicidal ideation and behavior, and vital signs to support the package insert for MDMA-assisted therapy. The following safety objectives will evaluate the safety of MDMA-assisted therapy:

1. Assess incidence of AEs during Experimental Sessions that may be indicative of a medical complication of the Investigational Medicinal Product (IMP) such as clinical signs and symptoms of chest pain, shortness of breath, or neurological symptoms or any other signs or symptoms that prompt additional vital sign measurements
2. Assess incidence of AEs by severity
3. Assess incidence of TEAEs by severity
4. Assess incidence of TEAEs by severity reported during an Experimental Session, 1 day, and 2 days after IMP administration
5. Assess incidence of AESIs, defined as AEs specified in the protocol related to cardiac function, suicidality, and abuse liability
6. Assess incidence of AEs by severity categorized as leading to discontinuation of IMP, resulting in death or hospitalization, and continuing at Study Termination
7. Assess incidence of SAEs
8. Assess incidence of concomitant medications taken during an Experimental Session, 1 day, and 2 days after IMP administration
9. Assess incidence of psychiatric concomitant medications taken during the Treatment Period
10. Assess incidence of positive or serious suicidal ideation and positive suicidal behavior assessed with the Columbia Suicide Severity Rating Scale (C-SSRS)
11. Assess changes in blood pressure (BP), heart rate, and body temperature from pre-IMP administration to end of each Experimental Session

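### SAP 8.8.4 leaves the counting unit of the suicidality table open and has no participant-level count of ideation or behavior that is new or worse after dosing

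*SAP*

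**What the plan says.** SAP 3.3, item 10, sets the target: "Assess incidence of positive or serious suicidal ideation and positive suicidal behavior", measured with the C-SSRS.

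SAP 8.8.4 then gives one specified statistic: "The number and percent of positive responses of Positive Ideation, Serious Ideation, and Positive Behavior will be tabulated", by time period. The periods are lifetime, screening, baseline, "each Experimental Session (pre- and post-IP), Integrative Sessions, and endpoints". The definition reads "A positive response for suicidal ideation is counted when a participant answers" yes to any of the five ideation questions; behavior is handled the same way. The section closes with "Frequency and incidence of positive or serious ideation and suicidal behavior will be presented using descriptive statistics in tabular format", and SAP 8.8.3 and Protocol 13.2.2 carry nearly the same sentence.

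SAP 8.4 takes the C-SSRS baseline from the Independent Rater Screening. Protocol 9.1, Table 9, says that after serious ideation or behavior the investigators are to "make additional follow-up C-SSRS observations to ensure participant safety and to track scores until they returned to non-serious levels".

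**The concern.** A percentage of responses and a percentage of participants are different quantities whenever a participant contributes more than one form to a period. SAP 8.8.4 uses the first expression and does not say which quantity is meant. For adverse events, SAP 8.8.2 has an explicit rule: one count per participant per preferred term, at the highest severity. The C-SSRS has no such rule. Two programmers could produce different tables from the same data and both follow the text.

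The second issue is what the table can show even when the unit is fixed. Each column is a total for one period. In a single-arm study with some ideation present at entry, the useful safety quantity is how many participants have ideation or behavior after dosing that they did not have, or had at a lower level, before dosing. Column totals do not give it. The safety objectives are meant to support the package insert, so the suicidality figures should have one meaning.

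**Working it through.** **Forms per period.** Protocol Table 6 allows 10 minutes per C-SSRS and 90 minutes at each Experimental Session visit. Two forms (pre and post) plus 14/2 = 7 calls make 9 forms, and 9 × 10 = 90 minutes, which reproduces the plan's figure. Protocol 7.3.3 gives three Integrative Sessions after each Experimental Session, each with one C-SSRS: 3 × 3 = 9 forms. Calls add up to 3 × 7 = 21 forms, fewer when an Integrative Session replaces a call.

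**Forms without a period.** The SAP 8.8.4 list has no entry for the phone calls or the triggered repeats. It also has no clear entry for the Visit 3 form, since SAP 8.4 places the C-SSRS baseline earlier. It itemises each Experimental Session but names Integrative Sessions once, and does not say whether the nine visits are pooled.

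**Effect of the unit.** Take N = 100 (the documents give about 100), n affected participants, m scheduled forms per participant in the period and k positive forms per affected participant.

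- Participants: n/N.
- Forms: nk/(Nm).
- Ratio of the first to the second: m/k.

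With n = 10 (assumed), the participant percentage is 10/100 = 10%. The form percentage is:

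- m = 1: 10/100 = 10%, no gap.
- m = 9, k = 1: 10/900 = 1.1%, ratio 9.
- m = 9, k = 3: 30/900 = 3.3%, ratio 3.
- m = 9, k = 9: 90/900 = 10%, no gap.
- m = 30 (Integrative Sessions and all calls together, 9 + 21), k = 1: 10/3000 = 0.33%, ratio 30.

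**Effect of triggered repeats.** The documents give no number of repeats. Assume 3 participants with one serious form each, and r further serious forms each, all falling in the pooled period. Participant incidence is 3/100 = 3% whatever r is. The form percentage is (3 + 3r)/(900 + 3r):

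- r = 0: 3/900 = 0.33%.
- r = 3: 12/909 = 1.3%.
- r = 6: 21/918 = 2.3%.
- r = 10: 33/930 = 3.5%.

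The two are equal when 3 + 3r = 27 + 0.09r, so r = 24/2.91 = 8.2. A form-based percentage therefore depends on how long serious ideation lasts and how often it is rechecked, as well as on how many people have it.

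**New or worse after dosing.** Three passages matter here. Exclusion criterion 10 in Protocol 3.2 sets thresholds for ideation scores of 4 and 5 and for recent behavior, so those thresholds do not bar lower ideation scores. Protocol Table 9 reports that scores rose during Preparatory Sessions in previous sponsor trials, possibly from preparation or medication taper. The SAP 8.4 baseline is taken before both. A rise between baseline and first dose could then look like a rise after dosing. The pre-IP column of the first session shows a later total, but totals do not identify people: 10 of 100 positive before dosing and 10 of 100 after is compatible with anything from 0 newly positive participants (the same 10) to 10 (no overlap).

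**The case against.** The strongest reply is that incidence is already planned. The sentence after the tabulation sentence commits to it, SAP 8.8.3 and Protocol 13.2.2 repeat it, and a positive response is defined by what a participant answers. SAP 8.8.4 also defers to the C-SSRS scoring guide, which may fix the unit and cannot be checked here. This stands to the extent that a reader who infers that the plan omits incidence, or that its denominator is forms, goes beyond the text. What remains is that none of these sentences states a denominator, a period or a repeat rule.

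Two further inferences are tempting and not supported. One is that the plan understates incidence up to ninefold. Nine is a scenario value that needs a form denominator, nine pooled visits and one positive form per affected participant; the ratio is 1 for single-form periods and can exceed 9 if calls are pooled in. The other is that triggered repeats inflate the result. On the figures above, 3 or 6 repeats per participant still leave the form percentage below the 3% of participants affected.

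It can also be said that objective 10 does not ask for within-participant change, and that SAP 8.8.2 separates pretreatment from treatment-emergent AEs, with serious ideation and suicidal behavior reported as AESIs under Protocol 10.1.3. That is fair: the new-or-worse count is an addition, not a missing promise. The AE route covers it only in part. Ideation scores below 4 are AESIs only if the investigator judges the ideation serious or severe, and the AESI line in SAP 8.8.2 names cardiac function and abuse liability but not suicidality.

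**Conclusion.** The point holds as an undefined unit, denominator and form assignment in SAP 8.8.4, together with a table that cannot separate ideation or behavior arising or worsening after dosing from what was present before. It does not hold as a finding that incidence has been left out.

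The size depends on the reading. It is zero if the table is by participant or by single visit. It is illustratively 1.1% against 10% if forms are counted over pooled Integrative Sessions and each affected participant is positive once. These figures assume N = 100, complete forms and 10 affected participants; they are not forecasts. The case for the new-or-worse count does not depend on them. It rests on what the entry criteria allow, where the baseline is placed and the escalation the protocol itself reports. This is an inexpensive improvement using data already collected.

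**What to change.** In SAP 8.8.4, replace the percentage of responses with the number and percent of participants with at least one positive form in the period, over participants with at least one C-SSRS in that period. Use the highest score per participant per period. Let scheduled, phone-call and triggered forms all contribute to the period in which they fall, and give the periods date limits so that each form falls in exactly one. Say whether Integrative Sessions are pooled, and place the Visit 3 form.

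Add the number and percent of participants whose highest score after the first dose is new or worse than their highest pre-dose score in this study, for ideation and for behavior, among participants with forms on both sides. The scheduled pre-dose forms in Protocol Table 6 are four: Screening, Independent Rater Screening, Visit 3 and pre-dose at Visit 4. A table note should say that the pre-dose and post-dose maxima rest on different numbers of forms and lengths of time, and that without a control group the count describes and does not attribute.

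The cost is SAP wording and one extra derivation, with no new data. Displayed percentages may be higher than a form-based table would show. The change should be made before the final analysis, so that the unit is not chosen with the results in view.

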### **8.8.5 Summary of Vital Signs**

Vital signs (heart rate, BP, and body temperature) for Experimental Sessions will be summarized using descriptive statistics in tabular format listing values at pre-IP, prior to the supplemental dose, and at the end of each Experimental Session. Change from Baseline in vital signs will be presented by study.

## **9.0 Timing of Analyses**

Preliminary analyses and listing reviews will be ongoing throughout the studies to inform therapist supervision and assumptions made for other and ongoing trials. For clinical study reports and publications, only locked database files will be used. The final analysis will be conducted after all participants complete Visit 20 and the database is locked.

